4.5 Pharmacokinetics

Blood samples for PK analysis of givinostat (ITF2357) and its major metabolites (ITF2374 and ITF2375) will be collected. There are 5 possible visits where the PK samples can be taken: Visits 7, 10, 11, 13 and 15.

All subjects will have a total of 6 PK specimens drawn during the study:

- Two samples drawn pre-dose. These 2 specimens must be drawn at different visits
- One sample drawn between 0 and 2 hours post-dose
- One sample drawn between 2 and 4 hours post-dose
- One sample drawn between 4 and 6 hours post-dose
- One sample drawn between 6 and 10 hours post-dose

PK parameters will be derived, where data allow, from the plasma concentration data for givinostat and its major metabolites. The actual sampling times will be used in the derivation of the PK parameters.

A listing will present details of PK assessments and plasma concentrations for the PK analysis set.

Details regarding population PK procedures, the derivation of PK parameters and further analyses and summaries of PK data will be given in a separate Population PK data analysis plan. Any evaluation of the relationship of givinostat PK exposure to efficacy and safety endpoints will also be documented separately to this SAP.

5 SAFETY EVALUATION

All safety listings will be presented for the all enrolled subjects set and all safety tables and figures will be presented for the safety analysis set unless specified otherwise. Additionally, see Section 2.8 regarding use of the target versus overall population. Baseline is defined as the last non-missing value recorded prior to or on the date of first study treatment. Where the value is recorded on the same date as first study treatment and there is no further information to confirm whether this was prior to start of treatment, the value will be considered prior to treatment if this was a screening or randomisation assessment and otherwise will be considered post treatment.

5.1 Adverse Events

Adverse events (AEs) will be coded using the MedDRA Dictionary Version 24.1.

A treatment-emergent adverse event (TEAE) is defined as an AE that started or worsened on or after the date of start of the administration of the IMP.

There will be no imputation of unknown dates for the calculation of duration or study day. However, for sorting and assignation, if the start date is unknown then it will be assumed to be treatment emergent unless the partial start date, or other data (i.e. stop date) indicates differently.

If the relationship to study drug is unknown, the AE will be assumed to be related to the study drug.

The total number of TEAEs and the total number of subjects with TEAEs, the total number of serious TEAEs and the total number of subjects with serious TEAEs, the total number of subjects with TEAEs leading to withdrawal, the total number of subjects with TEAEs leading to permanent discontinuation with IMP, the total number of subjects with TEAEs leading to temporary discontinuation with IMP, the total number of subjects with TEAEs leading to dose reduction, the total number of subjects with TEAEs leading to death, the number of subjects with TEAEs by severity and relationship to study drug will be summarised.

If a subject experienced more than one TEAE, the subject will be counted once at the worst severity and at the most related event.

The following summary tables will be produced for each treatment group by MedDRA system organ class (SOC) and preferred term (PT) within each SOC:

- total number of TEAEs and the total number of subjects with TEAEs
- total number of serious TEAEs and the total number of subjects with serious TEAEs
- total number of subjects with TEAEs leading to withdrawal
- total number of subjects with TEAEs leading to permanent discontinuation with IMP

- total number of subjects with TEAEs leading to temporary discontinuation with IMP
- total number of subjects with TEAEs leading to dose reduction
- total number of subjects with TEAEs leading to death
- total number of subjects with serious TEAEs leading to withdrawal
- total number of subjects with TEAEs by severity (Grade 1 Mild, Grade 2 Moderate, Grade 3 Severe or medically significant but not immediately life-threatening, Grade 4 Severe or life-threatening, Grade 5 Death related to AE)
- total number of subjects with TEAEs by relationship to study drug (related to study drug, not related to study drug)
- total number of subjects with TEAEs by steroid type at baseline (deflazacort, prednisone, other)

For all of the above, SOC and PT will be presented in decreasing frequency of the total number of subjects with TEAEs and then alphabetically.

Further details of the above tables are given below:

1. If a subject experienced more than one TEAE, the subject will be counted once for each SOC and once for each PT.
2. If a subject experienced more than one TEAE, the subject will be counted once for each PT.
3. If a subject experienced more than one TEAE, the subject will be counted once for each SOC and once for each PT at the worst severity.
4. If a subject experienced more than one TEAE, the subject will be counted once for each SOC and once for each PT using the most related event.

A by-subject AE data listing including verbatim term, coded term, treatment group, severity, time of onset and cessation of event, whether the AE was serious, action taken with study drug, other action taken, outcome and relationship to study treatment will be provided. The dose at onset of each AE will also be presented. Where a partial AE start date is recorded and there is more than one dose recorded during the possible period of AE onset, the maximum recorded dose taken during this time is presented.

In addition, the number and percentage of subjects with bronchopulmonary AEs (BAEs) will be presented by treatment group. Events considered to be BAEs will be identified via a medical review conducted prior to database lock (interim and final analyses) or data extract for safety reviews. BAEs will include but are not limited to respiratory tract infections involving the larynx, trachea, bronchi, lower airways or lung. As a conservative approach, more generic conditions, such as AEs recorded as 'respiratory tract infection', will be included. Where 'Influenza' events have been recorded, the concomitant presence of relevant respiratory symptoms (i.e. cough, laryngitis, bronchitis) will be verified in order to determine whether to count as a BAE. This table will also include the number and percentage of subjects who were given antibiotics for BAEs and a summary of the duration of antibiotic use for BAEs by treatment group. Antibiotics given for BAEs will be identified via medical review prior to database lock for the final analysis and interim analyses as needed. Duration of

antibiotic use for BAEs (months) will be calculated for each subject in relation to these identified antibiotics as:

Total duration of antibiotic use for BAEs – Total interruption in antibiotic use for BAEs where total duration of antibiotic use for BAEs is calculated as:

Last antibiotic end date – First antibiotic start date + 1

and total interruption in antibiotic use for BAEs is calculated as the sum of any time that antibiotics were not taken for BAEs between the first antibiotic start date and the last antibiotic end date.

Serious AEs, AEs leading to permanent discontinuation of IMP and AEs leading to dose reduction or permanent discontinuation of IMP will be listed separately.

5.2 Clinical Laboratory Evaluation

For each laboratory parameter, the baseline value will be defined as the last non-missing scheduled or unscheduled value available prior to or on the date of first study treatment. Where the value is recorded on the same date as first study treatment and there is no further information to confirm whether this was prior to start of treatment, the value will be considered prior to treatment if this was a screening or randomisation assessment and otherwise will be considered post treatment. If no measurement is recorded prior to first study treatment administration, the baseline value will be considered missing.

5.2.1 Hematology

Hematology parameters will be measured in Système International (SI) units at all EU sites and in US conventional units at all US sites. All results will be converted to SI units for the purposes of summaries, plots and listings. Summary statistics of hematology observed values and change from baseline by parameter and visit will be presented by treatment group for all subjects in the safety analysis set.

In addition, the following summaries in relation to post-baseline platelet counts will be presented by treatment group: minimum values, time to nadir (days) and time to recovery (days). These will be defined as follows:

Minimum value = minimum post-baseline platelet count for the subject.

Time to nadir (days) = time to first minimum value post-baseline regardless if this is within the normal range.

Time to recovery (days) = for subjects whose minimum post-baseline value is below the lower limit of normal, the time to recovery is calculated as the time from the minimum value below lower limit of normal to the first value within the normal range.

Furthermore, a table will be presented for subjects in the safety analysis set who reduced dose due to platelet count decrease which will summarise the following in relation to post-baseline platelet counts by treatment group: minimum values, time to nadir (days), time to recovery (days), time on treatment after recovery (days), additional platelet decrease after recovery, time on treatment without recovery (days), where:

Time on treatment after recovery = for subjects who record recovery from the minimum value below the lower limit of normal, the time on treatment after recovery

is calculated as the time from the date of recovery to the last treatment date or date of data cut-off.

Additional platelet decrease after recovery = number of subjects who record recovery from the minimum value below the lower limit of normal and then record a subsequent value below the lower limit of normal.

Time on treatment without recovery = for subjects who do not record recovery from the minimum value below the lower limit of normal, the time on treatment without recovery is calculated from the date of the minimum value below the lower limit of normal to the last treatment date or date of data cut-off.

A plot of the mean platelet count at each visit will be produced by treatment group.

Shift in hematology values from baseline to each visit for low, normal, high and total results based on reference ranges will be summarised by treatment group.

A box and whisker plot will present the results for the following parameters over time by treatment group: platelets, hemoglobin, neutrophils, leukocytes.

All hematology values will be listed, flagging all abnormal findings.

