**Dose Modification (all subjects):**

If subjects (i.e. those already in treatment or those who will be randomized under protocol version 6.0 or 7.0 or 8.0) gain weight during the study the drug dose must be kept unchanged.

If subjects (i.e. those already in treatment or those who will be randomized under protocol version 6.0 or 7.0 or 8.0) lose weight during the study, the drug dose should be adjusted

according to Table 2 or Table 3 if the subject is still on treatment at starting dose, or according to Table 4 or Table 5 if the subject has already reduced the starting dose.

All subjects will be asked to have platelets count assessments weekly during the first month of treatment and performed every two weeks during the second month of treatment, in order to strictly monitor this parameter for safety reasons.

If the dose is reduced due to platelet count  $\leq 150 \times 10^9/L$ , and/or white blood cell  $< 3.0 \times 10^9/L$  and/or hemoglobin  $< 10.0 \text{ mg/dL}$  a complete blood count (i.e.CBC) test must be performed weekly for 8 consecutive weeks.

If a dose adjustment and/or modification of schedule of assessments is decided by the Investigator or authorized designee, it is advised to discuss this decision with the Medical Monitor, however this is not mandatory as the Investigator is the only responsible for the medical care of the subject and the Investigator's decision should not be influenced, deleted nor approved by the Medical Monitor.

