6. 12-lead ECG has to be done in triplicate at the screening visit and during the other visits if an ECG demonstrates a prolonged QTcF interval  $>$  450 msec, obtain 2 more ECGs over a brief period, and then use the averaged QTcF values of the 3 ECGs to determine whether the subjects should be discontinued from the study (see Section 7.3.1). 12-lead ECG should be performed at 2,5 hours (i.e 150 minutes)  $\pm$ 30 minutes after drug intake.
7. Pulmonary function tests FEV1, FVC, FEV1/FVC and PEF. In case the test does not achieve ATS criteria and the evaluator does not feel a valid attempt has been made, the subject should repeat the test at randomization if the test is failed at screening visit. If the test is failed at 12 months and/or at 18 months the subject has to be asked to come back to perform the test.
8. Serology: immunoassay methodology for CMV IgM; in-house methodology of chemiluminescence for HBsAg/HCV/HIV; and ECLIA for EBV IgG.
9. Hematology test: CBC:RBC, WBC (including differential count), hemoglobin, MCH, MCHC, MCV, hematocrit, and platelets. Test will be done according to the schedule (i.e., weekly for the first month of treatment, every 2 weeks for the second month of treatment) and are to be performed more frequently if clinically indicated. Note: Repeat visits for the platelets count will be assumed at the request of the Investigator. If the dose is reduced due to platelet count  $\leq$ 150 x 10^9/L, and/or white blood cell  $<$ 3.0 x 10^9/L and/or hemoglobin  $<$ 10.0 mg/dL, a complete blood count (i.e.CBC) test must be performed weekly for 8 consecutive weeks.
10. The following blood tests will be assessed: total bilirubin, direct bilirubin, alkaline phosphatase, amylase, ALT, AST, LDH, cystatin C, CRP, GGT, creatine kinase, total protein, albumin, uric acid, triglycerides, phosphorus, total cholesterol, LDL, HDL, sodium, potassium, chloride, calcium, glucose, creatinine, BUN, TSH, fT3, fT4, bicarbonate). Note that TSH, fT3, and fT4 will be taken at Visits 7, 9, 10, 11, 12, 13, 14, 15 and 16.
11. Urinalysis: appearance, pH, specific gravity, protein, glucose, ketone bodies, blood and WBCs, and urobilinogen.

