1 INTRODUCTION

This statistical analysis plan (SAP) is based on protocol version 8.0 (and 8.1 for France use only) dated 8th April 2020 and Version 8.1 for Germany use only dated 25th June 2020 and will be finalised prior to full study unblinding. Any additional details or amendments will be discussed with Italfarmaco and included in a revised version of the SAP.

The table, figure and listing shells will be supplied in a separate document.

The analysis and statistical reporting will be conducted at Veristat using SAS version 9.2 or higher.

Summary statistics will consist of number of subjects (n), mean, standard deviation (SD), minimum, first quartile, median, third quartile and maximum, unless specified otherwise. The precision of these variables is defined in the table, figure and listing shells document.

Unless stated otherwise, for example in Section 4.4.4, missing data will be considered missing at random and there will be no imputation of missing data.

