2.8 Data presentations

The data will be summarised in tabular form by treatment group apart from disposition of subjects, protocol deviations, background and demographic data, administration of investigational medicinal product (IMP), plasma concentrations of givinostat and its major metabolites, prior and concomitant medications, which will be summarised by treatment group and overall subjects.

Only scheduled post-baseline laboratory, vital signs and electrocardiogram (ECG) values will be tabulated, post-baseline repeat/unscheduled assessments will be listed.

Listings will be sorted by treatment group, subject number and date/time of assessment.

Treatment groups will be presented in the following order: Givinostat, Placebo.

Graphical presentations of the data will also be provided where appropriate.

All efficacy analyses and data summaries will be presented for the target population only. Safety data will only be summarised for the overall subject population. Data summaries for disposition of subjects, protocol deviations, background and demographic data, administration of IMP, ankle range of motion, modified MRC grade and genotype data will be presented for both the target and overall subject populations. Presentation of analyses and summaries of PK data will be discussed in a separate Population PK data analysis plan (see Section 4.5).

Listings will be presented for the overall subject population. Inclusion of each subject in the target or off-target population will be indicated in the listing of analysis set assignments for reference. Listings for efficacy and PK data will also present patients sorted by target or off-target population for each treatment group.

The target population will serve as the basis for any formal analysis of efficacy.

Any further repeats of the data summaries and analyses for target, off-target or overall subject populations may be considered at a later date and included post hoc. Details of any such repeats will be included in a SAP addendum as appropriate.

Where data are imputed according to the rules defined in [Section 4.4.4](#), the imputed data will be used in all data presentations and analyses. Imputed values for efficacy data will be flagged in the listings with an indication of the missing data classification as applicable.

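### SAP 5.2.1 does not settle whether off-schedule counts enter the platelet nadir and recovery tables, and plans non-recovery and relapse results only for boys dose-reduced for platelets

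*SAP*

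**What the plan says.** SAP 2.8 sets a general rule: "Only scheduled post-baseline laboratory, vital signs and electrocardiogram (ECG) values will be tabulated, post-baseline repeat/unscheduled assessments will be listed".

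SAP 5.2 departs from it expressly for baseline, which is "defined as the last non-missing scheduled or unscheduled value available prior to or on the date of first study treatment". The post-baseline definitions in SAP 5.2.1 have no such wording. The nadir rests on "Minimum value = minimum post-baseline platelet count for the subject", and recovery time, for boys whose minimum is below the lower limit of normal (LLN), is "calculated as the time from the minimum value below lower limit of normal to the first value within the normal range".

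The all-subject table holds three items by arm: minimum value, time to nadir and time to recovery. Further items (time on treatment after recovery, a further fall below LLN after recovery, time on treatment without recovery) appear only in a second summary: "a table will be presented for subjects in the safety analysis set who reduced dose due to platelet count decrease". SAP 5.2.2 carries the same definitions over to triglycerides, with the direction reversed.

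The protocol generates many counts outside the visit schedule:
- After a dose reduction for low counts, section 8.2.2 says a complete blood count "test must be performed weekly for 8 consecutive weeks". Table 6, footnote 9, repeats this, just after noting that "Repeat visits for the platelets count will be assumed at the request of the Investigator".
- After a temporary stop, section 7.3.1 requires a platelet count within a week, then retesting until normal.
- At a count of 50 x 10^9/L or lower, section 7.3.1 requires a repeat on the next working day.

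Neither document labels these counts scheduled or unscheduled. SAP Addendum 1 does not touch the point.

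**The concern.** The counts whose status is unclear are the ones taken to follow a low platelet value. If they are left out:
- The tabulated minimum can sit above the true one, and a boy whose only count below LLN was a retest does not enter the recovery summary at all.
- Recovery is dated to the next scheduled visit with an in-range value, so it can look longer than it was. If the boy is low again by that visit, the recovery in between is not seen.

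In the all-subject table, recovery time exists only for boys with a later in-range value. The default statistics in SAP section 1 include n, so the number recovered will show. But SAP 5.2.1 specifies no count of boys below LLN who did not recover, or who fell below it again.

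Protocol 4.2.2 names thrombocytopenia among the most common adverse events. Protocol 8.2.1 says the starting dose was lowered after roughly 50 to 60% of boys with at least 8 weeks of treatment had to reduce dose for platelets. How long low counts last, and whether they return, is therefore something readers will look for. SAP 4.4.6.3 repeats the hematology summaries by weight-adjusted exposure and by starting dose, so the ambiguity carries into those comparisons.

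**Working it through.** The plan gives no figure on this point to reproduce. The check is date arithmetic on the schedule.

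**Inputs**
- Scheduled post-baseline hematology on treatment (Protocol Table 6): Weeks 1, 2, 3, 4, 6, 8, 12, 24, 36, 48, 60 and 72.
- Expected nadir: 2 to 3 weeks into treatment, then a plateau (Protocol 4.2.2).
- True recovery time R: 14 or 21 days from nadir. This is an assumption. Protocol 4.2.2 reports resolution within 2 to 3 weeks of stopping treatment, which is a different starting point.

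**Step 1. How many of the eight weekly counts fall on scheduled visits?** For a reduction at Week r, the counts are due at Weeks r+1 to r+8.
- r = 2: Weeks 3, 4, 6, 8, so 4 of 8
- r = 3: Weeks 4, 6, 8, so 3 of 8
- r = 4: Weeks 6, 8, 12, so 3 of 8
- r = 6: Weeks 8, 12, so 2 of 8
- r = 8: Week 12, so 1 of 8
- r = 12 (Weeks 13 to 20) and the later 12-weekly visits up to Week 60: 0 of 8

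**Step 2. Recovery as tabulated on scheduled values only.** For a nadir on day d, tabulated recovery = (first scheduled day at or after d + R) minus d. Excess = tabulated recovery minus R.

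| Nadir | R = 14 | R = 21 | Excess (days) |
|---|---|---|---|
| Week 2 (day 14) | 28 - 14 = 14 | 42 - 14 = 28 | 0, 7 |
| Week 3 (day 21) | 42 - 21 = 21 | 42 - 21 = 21 | 7, 0 |
| Week 4 (day 28) | 42 - 28 = 14 | 56 - 28 = 28 | 0, 7 |
| Week 6 (day 42) | 56 - 42 = 14 | 84 - 42 = 42 | 0, 21 |
| Week 8 (day 56) | 84 - 56 = 28 | 84 - 56 = 28 | 14, 7 |
| Week 12 (day 84) | 168 - 84 = 84 | 168 - 84 = 84 | 70, 63 |

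Nadirs at Weeks 24, 36, 48 and 60 give the same 84 days, because visits stay 12 weeks apart. With the 7-day windows at both visits, the Week 12 case runs from (168 - 7) - (84 + 7) = 70 days to (168 + 7) - (84 - 7) = 98 days.

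A Week 72 nadir is different. The only later scheduled count is the Week 76 follow-up, 28 days on, and Protocol 9.1.9 limits that visit to boys not entering the long-term study.

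**Step 3. The same boys with weekly counts included.** Recoveries of 14 and 21 days are recorded as about 14 and 21 days at any nadir week.

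**Step 4. Who is outside the dose-reduced table?** Boys with isolated low counts that never triggered a reduction, and boys stopped permanently at a confirmed count of 50 x 10^9/L or lower without an earlier reduction. For them SAP 5.2.1 plans no result on non-recovery or relapse.

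**The case against.** The strongest reply is that SAP 2.8 may not exclude these counts at all. The weekly counts are mandatory and written into a Table 6 footnote, so they can be read as scheduled. The definitions in SAP 5.2.1 are specific and unrestricted, and a derived time per boy is arguably not a tabulated visit value. This stands as far as it goes: a reader might infer a settled decision to discard retests, and the documents do not show one. They support two readings that give different tables, and the express mention of unscheduled values for baseline alone favours the narrower one.

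Second, the protocol expects the nadir at 2 to 3 weeks, when visits are close together. That also stands. A reader might infer that recoveries will typically be reported as 84 days. The documents do not support this, since that figure needs a nadir at Weeks 12 to 60 and an assumed recovery clock.

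Third, much is covered elsewhere. Consistent counts at or below 150 x 10^9/L require a dose reduction, which brings the boy into the second table. Boys stopped permanently are followed to resolution or stabilisation. Adverse events are tabulated by arm with outcomes listed (SAP 5.1), the duration of the first interruption is summarised (SAP 3.5), and shift tables and full listings are planned. The IDMC receives patient plots and per-subject listings. This coverage is real but partial. None of these tables gives the number of boys below LLN who did not recover or became low again, by arm, for everyone affected. The dose-reduced group is selected after randomisation by the platelet fall itself, so it makes a weak comparison between arms.

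The table shells are a separate document and were not available. They may already contain some of these rows.

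**Conclusion.** The concern holds as a gap in a descriptive safety derivation. On the literal reading of SAP 2.8, recovery is overstated by 0 to 7 days for the expected nadir and by up to 21 days for a Week 6 nadir. For nadirs at Weeks 12 to 60 it is tabulated as about 84 days. The visit arithmetic is exact; the 14 or 21 days from nadir is assumed.

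The missing counts of non-recovery and relapse are a separate gap, and its size cannot be fixed from the documents. They give neither the LLN nor the distribution of platelet counts, and the reduction trigger is described only by example. Any percentage of boys missed would depend on assumed inputs, and the range includes zero.

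Nothing here affects the primary analysis, the stopping rules or the data collected. All values are listed, so the tables can be corrected.

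**What to change.** In SAP 5.2.1, by addendum:
1. State that the platelet minimum, time to nadir, recovery and relapse derivations use scheduled and unscheduled values, as an exception to SAP 2.8.
2. For all boys with a post-baseline count below LLN, report by arm the number affected, the number not recovered, and the number below LLN again after recovery.

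In SAP 5.2.2, make the same two changes for triglycerides above the upper limit of normal. Protocol 7.3.1 requires two-weekly tests there after a stop, so the same question arises.

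A Kaplan-Meier summary of recovery time by arm, censoring unrecovered boys at their last value, is optional. It is expected to change the median little.

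The cost is one sentence in each section, a few count rows in the shells and modest programming. No new data are needed, and the sponsor has already used an addendum to correct derivations.
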